22.4. Potentially clinically significant ranges – Adolescents

Approved 10-Nov-2022 00:00:00

Test Parameter	Reference range (as per Lab Manual)		Potentially Clinically Significant Ranges (min and/or max limits)	SI Units
	LLN	ULN		
SERUM				
White Blood Cell Count (WBC)	4.00	10.70	<3 at post-baseline and ≥3 at baseline >15.0 at post-baseline and ≤15 at baseline	x10E9/L
Neutrophils (absolute)	1.60	7.40	<1.5 at post-baseline and ≥1.5 at baseline >9 at post-baseline and ≤9 at baseline	x10E9/L
Eosinophils (absolute)	0.00	0.70	>0.7 at post-baseline and ≤0.7 at baseline	x10E9/L
Basophils (absolute)	0.00	0.20	>0.2 at post-baseline and ≤0.2 at baseline	x10E9/L
Monocytes (absolute)	0.10	0.90	>0.9 at post-baseline and ≤0.9 at baseline	x10E9/L
Lymphocytes (absolute)	1.00	4.00	<0.8 at post-baseline and ≥0.8 at baseline >4.0 at post-baseline and ≤4.0 at baseline	x10E9/L
Hemoglobin				
*Male	114.00	* 175.00	<100 g/L at post-baseline and ≥100 g/L at baseline >200 g/L at post-baseline and ≤200 g/L at baseline	g/L
**Female		** 160.00		
Hematocrit				
*Male	0.36	* 0.52	<0.30 at post-baseline and ≥0.30 at baseline >0.6 at post-baseline and ≤0.6 at baseline	L/L
**Female		** 0.46		
Platelets	150.00	420.00	<100 at post-baseline and ≥100 at baseline	x10E9/L

This document is confidential.

1.0

CD14152.SPR118161.SAP.V01

Approved 10-Nov-2022 00:00:00

			>700 at post-baseline and ≤700 at baseline	
Sodium	135.00	148.00	<129 at post-baseline and ≥129 at baseline >150 at post-baseline and ≤150 at baseline	mmol/L
Potassium	3.50	5.30	<3.5 at post-baseline and ≥3.5 at baseline >5.5 at post-baseline and ≤5.5 at baseline	mmol/L
Calcium - total	2.14	2.62	<2 at post-baseline and ≥2 at baseline	mmol/L
Chloride	98.00	110.00	<95 at post-baseline and ≥95 at baseline >115 at post-baseline and ≤115 at baseline	mmol/L
Glucose	3.90	6.90	<3 at post-baseline and ≥3 at baseline >13.9 at post-baseline and ≤13.9 at baseline	mmol/L
Creatinine	31.00	106.00	> 1.5 x ULN 1st IMP dose and ≤ 1.5 x ULN 1st IMP dose	µmol/L
Blood urea nitrogen (BUN)	1.80	7.14	>7.14 at post-baseline and ≤7.14 at baseline	mmol/L
AST	0.00	41.00	>3 x ULN at post-baseline and ≤3 x ULN at baseline	U/L
ALT *Male **Female	5.00	* 30.00 ** 20.00	>3 x ULN at post-baseline and ≤3 x ULN at baseline	U/L U/L
Alkaline phosphatase *Male **Female	0.00	* 389.00 ** 186.00	>2.5 x ULN at post-baseline and ≤2.5 x ULN at baseline	U/L
Bilirubin total	0.00	21.00	>1,5 x ULN at post-baseline and ≤1,5 x ULN at baseline	µmol/L
CPK *Male **Female	2.00	* 251.00 ** 147.00	>2.5 x ULN at post-baseline and ≤2.5 x ULN at baseline >2.5 x ULN at post-baseline and ≤2.5 x ULN at baseline	U/L U/L
GGT *Male **Female	0.00	* 42.00 ** 24.00	>2.5 x ULN at post-baseline and ≤2.5 x ULN at baseline >2.5 x ULN at post-baseline and ≤2.5 x ULN at baseline	U/L U/L
Protein total	60.00	85.00	<50 at post-baseline and ≥50 at baseline >95 at post-baseline and ≤95 at baseline	g/L
Albumin	32.00	55.00	<30 at post-baseline and ≥30 at baseline	g/L
Uric acid *Male **Female	* 0.18 ** 0.13	* 0.51 ** 0.45	>0.51 at post-baseline and ≤0.51 at baseline >0.45 at post-baseline and ≤0.45 at baseline	mmol/L mmol/L
Cholesterol total	0.00	5.17	>7.75 at post-baseline and ≤7,75 at baseline	mmol/L
Triglycerides	0.00	2.25	>3.42 at post-baseline and ≤3,42 at baseline	mmol/L
VITAL SIGNS and WEIGHT				
Pulse rate	N/A	N/A	≤50 bpm and decrease from baseline ≥20 bpm ≥110 bpm and increase from baseline ≥20 bpm	beats/min
Diastolic blood pressure	N/A	N/A	≤50 mmHg and decrease from baseline ≥10 mmHg ≥90 mmHg and increase from baseline ≥10 mmHg	mmHg
Systolic blood pressure	N/A	N/A	≤90 mmHg and decrease from baseline ≥20 mmHg ≥135 mmHg and increase from baseline ≥20 mmHg	mmHg
Weight	N/A	N/A	≥5% increase from baseline ≥5% decrease from baseline	kg

This document is confidential.

118161_Galderma_SAP_Final_1.0_Version_09 NOV2022

Final Audit Report

2022-11-10

Created:	2022-11-10
By:	PPD
Status:	Signed
Transaction ID:	PPD

CD14152.SPR118161.SAP.V01 "118161_Galderma_SAP_Final_1.0_Version_09NOV2022" History

-  Document created by PPD
2022-11-10 - 8:42:29 AM GMT
-  Document emailed to PPD for signature
2022-11-10 - 8:45:36 AM GMT
-  Document emailed to PPD for signature
2022-11-10 - 8:45:36 AM GMT
-  Document emailed to PPD for signature
2022-11-10 - 8:45:36 AM GMT
-  Signer [contact] entered name at signing as [name]
2022-11-10 - 8:46:33 AM GMT
-  [name] ([contact]) verified identity with Adobe Acrobat Sign authentication
2022-11-10 - 8:46:35 AM GMT
-  Document e-signed by PPD
Signing reason: I am the author
Signature Date: 2022-11-10 - 8:46:35 AM GMT - Time Source: server
-  Email viewed by PPD
2022-11-10 - 9:12:03 AM GMT
-  Signer PPD
2022-11-10 - 9:17:48 AM GMT
-  PPD verified identity with Adobe Acrobat Sign authentication
2022-11-10 - 9:17:50 AM GMT

Approved 10-Nov-2022 00:00:00

Powered by
Adobe
Acrobat Sign

Document e-signed by PPD

Signing reason: I am the approver

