8.3 Selection of Study Population

8.3.1 Number of Planned Subjects

Approximately 750 total subjects are planned to be randomized, including a minimum of 130 adolescent subjects aged 12 to 17 years.

Refer to Section 10.2 for the statistical considerations on which the sample size is based.

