Shift tables will be generated using the reference ranges (Low, Normal, High and Missing) for hematology and chemistry laboratory data. The number and percentage of subjects shifting from reference ranges between Baseline and each visit (scheduled visits only) will be summarized for the Initial Period and the Maintenance Period. In addition, shift table from Week 16 will be provided for the Maintenance Period. Last, worst and maximum post baseline values will also be included in the shift tables and will include unscheduled visits in the derivation. Worst post baseline value will be defined as the highest or lowest value relative to the reference range.

Summary of the number and percentage of subjects who met criteria of potential clinically significant (CS) value will be summarized (scheduled visits only) for hematology and chemistry laboratory data. Last, worst and maximum post-baseline results will also be included in the summary. Potentially CS ranges for adult and adolescent are listed in sections 22.3 and 22.4.

For statistical and graphical summaries of the laboratory tests, values below or above the limit of detection (e.g. ' < 3 ' or ' > 500 ') are substituted with the lower limit of detection minus 1% for values below the lower limit and are substituted with the upper limit of detection plus 1% for values above the upper limit (e.g. ' < 3 ' is substituted by ' 2.97 ', ' > 500 ' is substituted by ' 505 '). In data listings, the values are shown including the $<$ or $>$ sign.

Distribution of Aspartate Aminotransferase (AST), Alanine Aminotransferase (ALT), Alkaline Phosphatase (ALP), Total bilirubin and Creatinine Phosphokinase (CPK) will be displayed graphically as boxplot by treatment group for each scheduled visit and the maximum post-Baseline (including unscheduled visits in the derivation) values for the Initial Period and the Maintenance Period.

By-subject listing will be presented for all laboratory data. By-subject listing for subjects with at least one abnormal result (out of reference range) will be provided for hematology and clinical chemistry. By-subject listing for subjects with at least one potentially CS result will be provided for hematology and clinical chemistry.

This document is confidential.

All laboratory data will be listed for the Safety population.

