22.3. Potentially clinically significant ranges – Adults

1.0

CD14152.SPR118161.SAP.V01

Approved 10-Nov-2022 00:00:00

Test Parameter	Reference range (as per Lab Manual)		Potentially Clinically Significant Ranges (min and/or max limits)	SI Units
	LLN	ULN		
SERUM				
White Blood Cell Count (WBC)	4.00	10.70	<3.0 at post-baseline and ≥3.0 at baseline >15.0 at post-baseline and ≤15 at baseline	x10E9/L
Neutrophils (absolute)	1.60	7.40	<1.5 at post-baseline and ≥1.5 at baseline >9 at post-baseline and ≤9 at baseline	x10E9/L
Eosinophils (absolute)	0.00	0.70	>0.7 at post-baseline and ≤0.7 at baseline	x10E9/L
Basophils (absolute)	0.00	0.20	>0.2 at post-baseline and ≤0.2 at baseline	x10E9/L
Monocytes (absolute)	0.10	0.90	>0.9 at post-baseline and ≤0.9 at baseline	x10E9/L
Lymphocytes (absolute)	1.00	4.00	<0.8 at post-baseline and ≥ 0.8 at baseline >4.0 at post-baseline and ≤ 4.0 at baseline	x10E9/L
Hemoglobin *Male **Female	* 135.00 ** 120.00	* 175.00 ** 160.00	* <100 g/L at post-baseline and ≥ 100 g/L at baseline * ≥200 g/L at post-baseline and < 200 g/L at baseline ** <90 g/L at post-baseline and ≥ 90 g/L at baseline ** ≥180 g/L at post-baseline and < 180 g/L at baseline	g/L
Hematocrit *Male **Female	* 0.40 ** 0.36	* 0.52 ** 0.46	<0.30 at post-baseline and ≥ 0.30 at baseline >0.6 at post-baseline and ≤ 0.6 at baseline	L/L
Platelets	150.00	350.00	<100 at post-baseline and ≥ 100 at baseline >700 at post-baseline and ≤ 700 at baseline	x10E9/L
Sodium	135.00	148.00	<129 at post-baseline and ≥ 129 at baseline >150 at post-baseline and ≤ 150 at baseline	mmol/L
Potassium	3.50	5.30	<3.5 at post-baseline and ≥ 3.5 at baseline >5.5 at post-baseline and ≤ 5.5 at baseline	mmol/L
Calcium - total	2.14	2.62	<2 at post-baseline and ≥ 2 at baseline	mmol/L
Chloride	98.00	110.00	<95 at post-baseline and ≥ 95 at baseline >115 at post-baseline and ≤ 115 at baseline	mmol/L
Glucose	3.90	6.90	<3 at post-baseline and ≥ 3 at baseline >13.9 at post-baseline and ≤ 13.9 at baseline	mmol/L
Creatinine *Male **Female	* 62 ** 44	* 106 ** 80	>1.5 x ULN at post-baseline and ≤1.5 x ULN at baseline	µmol/L
Blood urea nitrogen (BUN)	2.1	8.9	>8.9 at post-baseline and ≤8.9 at baseline	mmol/L
AST	0.00	41.00	>3 x ULN at post-baseline and ≤3 x ULN at baseline	U/L
ALT	0.00	45.00	>3 x ULN at post-baseline and ≤3 x ULN at baseline	U/L
Alkaline phosphatase *Male **Female	* 40 ** 35	* 129 ** 104	>2.5 x ULN at post-baseline and ≤2.5 x ULN at baseline	U/L

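### As written, the adolescent creatinine criterion in SAP 22.4 contradicts itself, so no adolescent can meet the potentially clinically significant flag for creatinine

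*SAP*

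**What the plan says.** SAP 22.4 tabulates the PCS limits for adolescents. The creatinine row gives a reference range of 31 to 106 µmol/L, not split by sex, and the criterion "> 1.5 x ULN 1st IMP dose and ≤ 1.5 x ULN 1st IMP dose".

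The adult creatinine row in SAP 22.3 reads ">1.5 x ULN at post-baseline and ≤1.5 x ULN at baseline". The adolescent rows next to creatinine follow that same pattern: blood urea nitrogen is ">7.14 at post-baseline and ≤7.14 at baseline" and AST is ">3 x ULN at post-baseline and ≤3 x ULN at baseline".

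These appendix tables drive outputs. Protocol 10.1.4.3 commits to counting subjects who meet PCS criteria by treatment group. SAP 13.2.1 carries this out and points to the appendix: "Potentially CS ranges for adult and adolescent are listed in sections 22.3 and 22.4". It adds: "By-subject listing for subjects with at least one potentially CS result will be provided for hematology and clinical chemistry". The table index names the outputs as 14.3.4.1.2.6 (initial period), 14.3.4.1.2.7 (maintenance period) and listing 14.3.4.1.2.9.

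Protocol 8.3.1 plans about 750 randomized subjects, "including a minimum of 130 adolescent subjects aged 12 to 17 years".

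**The concern.** A PCS criterion for a laboratory value is meant to pick out subjects who were within the limit before treatment and went beyond it afterwards. That needs two time points. The adolescent creatinine row names only one, the first dose, and asks for a value both above and not above the same limit there.

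No other definition of this flag exists in the documents. SAP section 15, which lists changes from the protocol, deals only with concomitant therapy. If the row is followed, the flag for this one analyte stays empty in adolescents whatever their data show. Because it is empty by definition, nothing in the output would tell a reader that the criterion had failed.

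**Working it through.** The plan states no figure to reproduce here, so this is a check of logic with a little arithmetic.

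**Inputs**
- Adolescent creatinine ULN: 106 µmol/L (SAP 22.4).
- Multiplier: 1.5 (same row).
- Planned adolescents: at least 130 of about 750 (Protocol 8.3.1).
- Randomization 2:1, stratified by IGA and PP NRS, not by age (Protocol 8.4.5).

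**Step 1: cut-off.** 1.5 × 106 = 159 µmol/L.

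**Step 2: the row as written.** Let x be creatinine at the first dose. The criterion is x > 159 and x ≤ 159. The two conditions are complementary, so their intersection is empty. On a grid from 0 to 400 µmol/L in steps of 0.5, 0 of 801 values qualify.

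**Step 3: the adult pattern with the same cut-off.** The criterion becomes post-baseline > 159 and baseline ≤ 159. On the same grid, 482 values lie above 159 and 319 at or below it, so 482 × 319 = 153,758 of 801² = 641,601 pairs qualify. That count is not a probability; it shows only that the rule can now be met. Examples:

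| Baseline | Post-baseline | As written | Adult pattern |
|---|---|---|---|
| 60 | 170 | not flagged | flagged |
| 60 | 150 | not flagged | not flagged |
| 165 | 170 | not flagged | not flagged |
| 170 | 60 | not flagged | not flagged |

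**Step 4: is the row an outlier?** Yes. Every other laboratory row in SAP 22.4 contrasts post-baseline with baseline. The pulse, blood pressure and weight rows have a different form, using change from baseline, and are not the comparator. No other row in 22.3 or 22.4 mentions a first IMP dose, and IMP is not in the SAP glossary.

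**Step 5: who is affected.** At the planned minimum, adolescents are 130/750 = 17% of subjects. At 2:1, about 130 × 2/3 = 87 would be on nemolizumab. This is an expectation only, since age is not a stratification factor.

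**Step 6: effect on a pooled percentage.** The index titles do not split the PCS tables by age. Suppose they are pooled and programmed literally. Adolescents then stay in the denominator but cannot enter the numerator. If adolescents and adults truly crossed the limit at the same rate, the table would show (750 − 130)/750 = 620/750 = 0.83 of the true percentage. If no adolescent crossed it, nothing would be lost. The equal-rate case is an assumption, because the documents give no expected rate.

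**The case against.** The strongest reply is that this is an obvious drafting slip with little consequence. Words such as *after* and *before* seem to have dropped out. The neighbouring rows show what was meant, and SAP section 18 requires programs to be checked for their logic. A programmer meeting an empty condition would probably notice and follow the adult row. Words lost when the PDF was read also cannot be fully excluded, although the row shows no gap or redaction.

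Much of this stands. The consequence depends on literal programming. But the SAP nowhere authorises using the adult wording instead, so a silent correction would be an undocumented departure from an approved plan.

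It is also fair to say that the information is not lost. SAP 13.2.1 plans continuous summaries that include worst and maximum post-baseline values. It plans shift tables: "Shift tables will be generated using the reference ranges (Low, Normal, High and Missing) for hematology and chemistry laboratory data". It plans a by-subject listing of every out-of-range chemistry result (14.3.4.1.2.8), whose trigger above ULN is lower than 1.5 × ULN and so would include anyone the PCS rule was meant to catch. Under Protocol 9.2.2, investigators assess out-of-range values and report clinically significant new or worsened ones as adverse events. What these do not provide is a count of subjects who newly crossed 1.5 × ULN: the shift tables stop at low, normal and high, and the out-of-range listing does not apply that cut-off.

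**Conclusion.** The row is wrong as written. If it is programmed literally, the creatinine PCS flag cannot be met by any adolescent in tables 14.3.4.1.2.6 and 14.3.4.1.2.7 or listing 14.3.4.1.2.9. A pooled creatinine PCS percentage is then understated by the number of adolescents who should have qualified. That number is unknown and could be zero.

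Three stronger readings are tempting, and the documents support none of them:
- A reader might infer that adolescents cannot be flagged for any laboratory abnormality. Only creatinine is affected; the other adolescent PCS rows can all be met.
- A reader might infer that the report will display a reassuring zero out of 130 or more adolescents. No such output is indexed. The PCS chemistry tables are for the whole safety population of each period, and the age-group safety summaries in SAP 13.1 cover adverse events only.
- A reader might infer that a renal signal in adolescents would be hidden. High values remain visible in the other outputs named above.

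The conclusion assumes that the printed row is the row in the signed SAP. It is a minor correction to one derived safety output, with no bearing on efficacy, power or alpha.

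**What to change.** Check the row against the signed copy of the SAP. If it reads as printed, replace the adolescent creatinine criterion in SAP 22.4 with the wording of the adult row, ">1.5 x ULN at post-baseline and ≤1.5 x ULN at baseline". The 1.5 × ULN cut-off and the adolescent reference range stay as the sponsor set them; only the time points change. The flag is a reporting rule and does not govern treatment.

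The cost is one line in the SAP, recorded as a correction, and one check that the PCS program for adolescent creatinine compares post-baseline values with baseline. No new data, tables or analyses are needed.
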